**8. We conducted a single center pilot study of a multimodal resiliency training program.**

A total of 27 ICU nurses participated and completed the 12-week trial (Intervention arm n=13, Control arm n=14). The resiliency program included four main components: 1) MBSR, 2) CBT, 3) writing therapy, and 4) exercise. Participants in the intervention arm also attended an introductory weekend session. During the informed consent process, control subjects were informed about psychological distress in ICU nurses. During the trial, control subjects also recorded the time spent performing aerobic exercise. All subjects completed pre/post psychological surveys. The intervention was successfully implemented in the treatment arm with 100% attendance at the introductory workshop, 100% completion of weekly writing sessions, 88% completion of the required exercise sessions (42% of the control group exercised at a rate similar to intervention subjects) and 100% attendance at CBT sessions. Using the client satisfaction measure, there was a high level of satisfaction with the program as evidenced by mean scores: 25.2 (SD 4.6) for the introduction session, 22.6 (SD 8.1) for written therapy, 28.2 (SD 4.3) for exercise and 24.5 (SD 5.4) for CBT. These scores demonstrate acceptability for our program

**9. Nurses randomized to the treatment group had increased resiliency scores and diminished PTSD and BOS symptoms.** Following completion of the 12 week trial, a repeated measure analysis demonstrated that the intervention was associated with increased resiliency, and decreased PTSD and BOS-emotional exhaustion scale (BOS data not shown in Figure 4). There were also modest improvements in the control subjects that may be related to interactions between subjects in the intervention and control groups, or problems with assessment reactivity. In our proposed pilot study, we will determine the proper level of randomization at either the individual or unit level. This work was published in the *American Journal of Critical Care* (AJCC) with a November 2014 press release. [name] was interviewed for the May 2015 Nursing Show.

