### **F. Data Analysis Plan:**

**Quantitative Statistical Analysis and Power Analysis:** For Aim #2.1, our primary outcome variable will be the post-pre change in CD-RISC scores in intervention and control subjects. Previous studies suggest that clinically significant changes in CD-RISC scores range from 12-19 points with an approximate standard deviation of 20 points. With a total enrollment of 160 subjects, we will be able to detect a difference of 12 points in CD-RISC score between the control and intervention groups with 90% power (assuming a 2-sided significance level (alpha) of 0.05 and an equal variance *t* test; software: PASS 13); we will be able to detect a difference of 19 points in CD-RISC score between the control and intervention groups with 100% power. We will also examine the change in MBI, PDS, and HADS scores in both the treatment and control groups. We will corroborate our comparisons of changes in all scores using robust bootstrap and permutation methods. When measuring constructs involving psychological mood, there is always concern that the answers reflect transient, less stable responses. The participant responses may simply change over time making certain paired analyses difficult to interpret. Therefore, we will calculate a coefficient alpha to estimate measurement reliability.

If we fail to find a bigger increase in CD-RISC score in the intervention group, as we expect, that may be due to interactions (contamination) between members of the intervention and control groups. We will assess the extent of contamination in Aim #2.2, for which our primary outcome variable will be the change in mean baseline CD-RISC score over time within each ICU. If there is, on average, greater than 30% contamination (that is, if baseline pre-enrollment CD-RISC scores increase), we will consider using a randomized cluster design for the subsequent multi-center clinical trial. If baseline CD-RISC scores increase 4 points over each intervention period, we will be able to detect that progressive increase with roughly 92% power (10,000 simulations using the Jonckheere-Terpstra ordered alternatives procedure; software: R). Our assessment of changes in baseline CD-RISC scores over time will consider the point and interval estimates of the changes in addition to formal statistical significance which may be of less use in this setting. All analyses will use SAS 9.3 and  $p < 0.05$  will be considered significant.

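### The Aim 2.2 contamination measure cannot see leakage into enrolled controls, cannot separate diffusion from a time trend, and never computes the 30% on which the design choice turns

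*Combined protocol and SAP*

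**What the plan says.** Aim 2b, in the Specific Aims, is to find the randomization level that best limits contamination between the arms. Section F (Data Analysis Plan) says that a missing difference in CD-RISC is something "that may be due to interactions (contamination) between members of the intervention and control groups". It then sends the assessment to Aim 2.2, "for which our primary outcome variable will be the change in mean baseline CD-RISC score over time within each ICU".

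The decision rule follows: "greater than 30% contamination (that is, if baseline pre-enrollment CD-RISC scores increase), we will consider using a randomized cluster design" for the later trial. Power is stated for one scenario, "If baseline CD-RISC scores increase 4 points over each intervention period", and is given as "roughly 92% power (10,000 simulations using the Jonckheere-Terpstra ordered alternatives procedure; software: R". The same paragraph adds that point and interval estimates will be considered alongside significance.

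The motivation is in Preliminary Studies, item 9, on the earlier single-center pilot: "There were also modest improvements in the control subjects that may be related to interactions between subjects in the intervention and control groups". Assessment reactivity is offered there as the other explanation.

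**The concern.** The plan describes one quantity and measures another. In an individually randomized trial, the harmful contamination is a gain by control nurses from colleagues in the MBCT arm. That is how Section F describes it, and it is where the earlier pilot suspected it. A control nurse's baseline is taken before randomization, so any gain after that point cannot enter the Aim 2.2 measure.

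The measure also runs along calendar time, over at least 10 months of successive waves. Changes in staffing, in season, or in which nurses volunteer first would move baseline means with no contamination at all. A downward trend of that kind would hide real diffusion. The plan describes no concurrent unexposed ICU, no calendar-time adjustment and no contrast between more and less exposed ICUs.

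Finally, the rule turns a percentage into a direction: "If there is, on average, greater than 30% contamination (that is, if baseline pre-enrollment CD-RISC scores increase". Nothing converts CD-RISC points into percent contamination.

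At stake is the choice between individual and cluster randomization for the multi-center trial, which is a named product of this pilot.

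**Working it through.** **Inputs.**
- From the Methods/Randomization paragraph: about 24 nurses per wave, five waves of two months.
- From Section F: a 4-point step per period, the Jonckheere-Terpstra test, significance at 0.05, a total of 160 nurses, a 12-point between-arm difference, and an "approximate standard deviation of 20 points".
- From the Inclusion Criteria: entry requires CD-RISC below 82.
- Assumed: SD 20 also holds for baseline scores (the plan gives it for changes); wave size is 24, or 160/5 = 32; sidedness, which is not stated for this test, is tried both ways.

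**Step 1: reproduce the stated power.** The statistic J counts pairs, one nurse from an earlier and one from a later wave, in which the later score is higher. Under no trend its mean is (N² − Σn²)/4 and its variance is [N²(2N+3) − Σn²(2n+3)]/72. For 5 × 24 (N = 120):
- mean = (14,400 − 2,880)/4 = 2,880
- variance = (14,400 × 243 − 2,880 × 51)/72 = 46,560, so SD = 215.8.

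Simulation with a 4-point step (10,000 runs) gives:

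| Waves | One-sided | Two-sided |
|---|---|---|
| 5 × 24 | 91.7% | 85.6% |
| 5 × 32 | 96.8% | 93.5% |

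The stated 92% is reproduced by 5 × 24 one-sided and, within 2 points, by 5 × 32 two-sided. Nothing in the calculation depends on why scores rise. A background rise of 4 points per period with zero contamination is therefore flagged with the same probability.

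**Step 2: a smaller background rise, zero contamination.** With a rise of 2 points per period, two waves d steps apart have P(later > earlier) = Φ(2d/(20√2)), which is 0.528, 0.556, 0.584 and 0.611 for d = 1 to 4. There are 4, 3, 2 and 1 such pairs of waves, each with 24 × 24 = 576 comparisons. The shift in J is 576 × (4 × 0.0282 + 3 × 0.0562 + 2 × 0.0840 + 0.1113) = 323, or 323/215.8 = 1.50 SD. The approximate signal rates are Φ(1.50 − 1.645) = 44% one-sided and Φ(1.50 − 1.96) = 32% two-sided. Simulation gives 45% and 33%.

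Those rates apply if the means are of all screened nurses. If they are of enrolled nurses, scores are cut off at 82 and drift is attenuated. With assumed uncut starting means of 65 to 80, simulation gives 20-28% one-sided and 12-18% two-sided. The cap also lowers power for the plan's own 4-point step, to about 47-67% (5 × 24, one-sided).

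**Step 3: leakage only into enrolled controls, baselines flat.** Suppose a share c of a 12-point effect reaches controls after their baseline. The baseline measure does not change, and the simulated flag rate is 4.4-5.5% for c = 0, 30%, 50% or 80%. The between-arm comparison does change. Its difference is 12(1 − c), with standard error 20√(2/n) for n nurses per arm:
- N = 120: SE = 20√(2/60) = 3.65. At c = 0, power = Φ(12/3.65 − 1.96) = 91%. At c = 0.3, power = Φ(8.4/3.65 − 1.96) = 63% (simulated 62%).
- N = 160: SE = 20√(2/80) = 3.16. At c = 0, power = 97%. At c = 0.3, power = 76% (simulated 75%).

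Leakage at the plan's own 30% level would thus cost the Aim 2.1 comparison much of its power while leaving the Aim 2.2 measure silent.

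**Step 4: what 30% could mean.** As a share of a 12-point effect, it is 0.30 × 12 = 3.6 CD-RISC points. The plan contains no such figure.

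**The case against.** Baseline drift is a reasonable proxy for diffusion through a unit. If trained nurses influence colleagues, those not yet enrolled should be affected too, and about half of them become later controls. This stands: the measure is informative. A reader might infer that it misses contamination altogether, but the documents do not support that. What it misses is leakage during a control nurse's own participation. The 5% figure describes the extreme case in which leakage reaches only enrolled controls, and nothing in the documents shows such confinement.

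The background rises are assumed. The documents give no secular trend, and 2 points per period amounts to 4 × 2 = 8 points from first to fifth wave, against a smallest clinically significant change of 12. The entry cap may also lower the signal rate. Both points stand, so Step 2 is an illustration and not a forecast.

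A reader might also infer that the rule fires half the time by chance, because a flat series drifts upward that often, or that a rise automatically forces a cluster design. Neither follows. The same paragraph supplies a trend test and interval estimates, and the team will only consider clustering. Intervals, however, express sampling error. They do not remove confounding with time or reveal leakage that was not measured.

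The qualitative interviews might help, but the questions listed under Outcome Measures cover helpfulness and coping; none listed there asks about contact between arms.

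**Conclusion.** The point holds and should be fixed. The Aim 2.2 measure does not match Section F's own account of contamination, is confounded with calendar time and order of volunteering, and is tied to a 30% threshold that is never calculated. The 92% is power to detect drift from any cause.

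For an assumed contamination-free rise of 2 points per period (5 × 24, SD 20), the signal rate is about 33% two-sided to 45% one-sided for all screened nurses. For enrolled nurses cut off at 82, it is about 12-18% to 20-28%. These rates depend on the assumed trend, baseline SD and starting means. The mismatch, the confounding and the undefined threshold do not depend on them.

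Two stronger conclusions should be resisted. The plan is not bound to reach the wrong randomization level, since the decision is a judgement using interval estimates. Nor does the choice of Aim 2.2 measure invalidate the CD-RISC comparison in Aim 2.1, which is analysed separately.

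**What to change.** Change the wording for Aim 2.2 in Section F:

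1. Define the 30% threshold in CD-RISC points as a share of the between-arm effect (for example, 3.6 points if the effect is 12), and delete the statement that equates it with a rise in scores.
2. Add an analysis of control-arm post-pre CD-RISC change by the number of MBCT-allocated nurses in the same ICU, adjusted for baseline CD-RISC, cohort and ICU. Report the estimate with its interval, not as a pass/fail test.
3. Keep baseline drift, but state whether it uses screened or enrolled nurses. Analyse it as a period-by-exposure contrast across ICUs, and say that an overall rise alone is not evidence of contamination.

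No new data are needed: allocation and post-pre CD-RISC are collected, and the planned within-ICU measure already requires each nurse's ICU.

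The cost is imprecision, which must be stated. Without the ICU term, simulation gives a standard error of about 1.3 to 1.8 points per trained colleague for an assumed 4 to 12 ICUs. As a ratio to a 12-point gain, the SD is about 108, 64 and 48 percentage points for 4, 8 and 12 ICUs. With zero contamination, the point estimate would exceed 30% in 36%, 31% and 23% of runs. An ICU term guards against differences between units but is likely to widen this further. The estimate can inform the choice of randomization level through its interval; it cannot settle it alone.

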## **G. Summarize Knowledge to be Gained:**

By creating sustainable change in an ICU nurse's ability to adapt to their work environment, we anticipate that our MBCT-ICU program will enhance nursing performance in an extremely stressful job; decrease BOS symptoms; and allow nurses to more effectively care for patients in the challenging ICU environment. The results of this study will be used as preliminary data to support a larger clinical trial to determine the effectiveness of the intervention.

